6.2 Randomization process

Patients will be randomized at the time of inclusion, in accordance with an automatically generated randomization list. One group will start treatment with a very low calorie and ketogenic diet (VLCK diet group) while the other group will start a low calorie diet (control group). The patient ratio in both groups will be 1: 1.

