7.4 Number of subjects

A total of 40 patients will be included: 20 patients randomly assigned to a very low-calorie-ketogenic diet (VLCK diet group) and 20 patients randomly assigned to low calorie diet (control group).

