7.5 Rationale of sample size

Exploratory pilot study to test a concept, where it has been estimated that 20 patients per group will be sufficient to analyze results.

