9 STUDY PROCEDURES AND OUTCOME MEASURES

9.1 Outcome measures

9.1.1 *Primary variables*

- Liver fatty infiltration, measured by a MRI technique of fat liver quantification (Ideal IQ**).
- Visceral fat, measured by the area in squared centimeters at the level of the 3rd vertebrae, using MRI technique.

9.1.2 *Secondary variable*

- Liver stiffness detected by MR Elastography
- Adrenal gland linear measurement
- Body weight
- Salivary cortisol levels

9.1.3 *End points*

- Reduction of fat infiltration into the liver between the baseline visit and 2 months (or end of the ketosis stage) and between the baseline visit and the control visit at month 6 of treatment.
- Visceral fat reduction between the baseline visit and 2 months (or end of the ketosis stage) and between the baseline visit and the control visit at month 6 of treatment.
- Correlation between degree of liver fat infiltration and liver stiffness
- Correlation between adrenal gland size and BMI, visceral fat and liver steatosis.
- Correlation between salivary cortisol levels and BMI, visceral fat and liver steatosis.
- Weight loss between the baseline visit and 2 months (or end of the ketosis stage) and between the baseline visit and the control visit at month 6 of treatment.

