9.2.2 Flow chart

	Pre-study	Onset	Visit at month 2 (end of ketosis)	Visit at month 6 (Final visit)
Review of inclusion and exclusion criteria.	X	X		
General blood test with liver function	X		X	X
Patient information	X			
Informed consent		X		
Comorbidities and medication		X	X	X
Anthropometric data (weight, BMI, WC)	X	X	X	X
MRI + MR Elastography		X	X	X
Salivary cortisol test		X	X	X
Adverse reactions			X	X
Drop outs and end of study			X	X

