10.2 Analysis of objectives

For the analysis of the primary objective and the secondary objectives, the differences between visits and between groups will be studied for the changes in the ratio between liver fat and the degree of steatosis (measured by MRI), changes in the degree of liver stiffness, changes in cortisol levels in saliva, weight changes, BMI and waist circumference, and changes in the amount of visceral fat among visits. The qualitative variables will be compared using Fisher's exact test, and the quantitative variables will be compared by means of the Student's t test for paired data. If the conditions to apply the Student's t test are not met, we will use the non-parametric Mann-Whitney U test. In the case of comparing paired data, we will use the tests described above, in their version for comparing this type of data.

The Pearson correlation coefficient or Spearman's correlation coefficient if the application conditions are not met will be used to study the following: the association between reduction of hepatic steatosis and weight loss and loss of visceral fat; the association between hepatic steatosis and liver stiffness; and the association between adrenal gland size and salivary cortisol levels with weight changes, BMI, hepatic steatosis and visceral fat.

For all tests, the significance level will be set at $p < 0.05$.

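### Section 10.2 compares unadjusted changes between arms and never uses each outcome's own baseline, giving up precision that baseline adjustment could recover at almost no cost

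*Combined protocol and SAP*

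**What the plan says.** Section 10.2 says that differences between visits and between groups will be studied for changes in liver fat, liver stiffness and then "changes in cortisol levels in saliva, weight changes, BMI and waist circumference, and changes in the amount of visceral fat among visits". Quantitative variables get a Student's t test, which the text describes as the paired one. The Mann-Whitney U test is the fallback, and a later sentence adds paired versions for paired data. The remaining analyses are Fisher's exact test for qualitative variables and Pearson or Spearman correlations. The section closes with "For all tests, the significance level will be set at" p < 0.05. No part of the document mentions a regression model, a covariate or any baseline adjustment of the arm comparison.

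Section 9.1.3 defines the endpoints as changes, for example "Visceral fat reduction between the baseline visit and 2 months (or end of the ketosis stage", and again from baseline to month 6. Liver fat and visceral fat are the two primary variables (9.1.1).

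All the baselines are collected. The flow chart (9.2.2) marks "Anthropometric data (weight, BMI, WC", MRI with MR elastography, and salivary cortisol at the onset visit.

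Allocation is "in accordance with an automatically generated randomization list" (6.2), 1:1, with no stratification described. Section 7.4 plans 40 patients, 20 per arm. Section 7.5 supports this only by saying that "it has been estimated that 20 patients per group will be sufficient to analyze results".

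**The concern.** A change score subtracts the whole baseline value. That is the best use of the baseline only if follow-up rises one for one with it. If the slope of follow-up on baseline is below 1, the change still depends on the starting value. Two things follow. Variation that the baseline could explain stays in the standard error. And if the arms happen to start apart, part of that gap appears as an apparent diet effect.

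Both matter more in a small trial. Nothing in the described randomisation balances these baselines, and eligibility runs from BMI 30 upward with only a 140 kg weight limit (7.2, 7.3), so starting values may vary widely. A pilot's main product is an estimate with its confidence interval, and precision is scarce at 20 per arm.

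**Working it through.** **Inputs from the documents.** 20 per arm (7.4), 1:1 allocation (6.2), significance level 0.05 (10.2; two-sided assumed).

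**Inputs not in the documents.** The correlation rho between baseline and follow-up, the SDs and the expected effects are absent. They are assumptions below, shown over a range. Section 7.5 gives no effect size, SD or power, so the figure of 20 per group cannot be reproduced.

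**Scale.** By the normal approximation, 20 per arm gives 80% power for a difference in change of about 0.89 SD of the change, and 35% for 0.5 SD.

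**General formula.** Let the baseline SD be s, the follow-up SD ks, and the slope of follow-up on baseline b = rho × k.
- Variance of change: s²(1 + k² − 2 rho k).
- Residual variance after adjustment: k²s²(1 − rho²).
- The first minus the second is s²(1 − b)². This is never negative, and it is zero only when b = 1.

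Estimating the slope multiplies the adjusted variance by about 1 + 1/(40 − 4) = 37/36.

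**Equal SDs (k = 1).** The ratio of adjusted to change-score variance is (1 + rho)/2 × 37/36. Patients per arm is the number the adjusted analysis needs to match 20 per arm on change scores. Power is for an effect that the change-score t test detects with 80% power.

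| rho | Variance ratio | Patients per arm | Power, adjusted |
|---|---|---|---|
| 0.5 | 0.75 × 37/36 = 0.77 | 15.4 | 89% |
| 0.7 | 0.85 × 37/36 = 0.87 | 17.5 | 85% |
| 0.8 | 0.90 × 37/36 = 0.93 | 18.5 | 83% |
| 0.9 | 0.95 × 37/36 = 0.98 | 19.5 | 81% |
| 0.95 | 0.975 × 37/36 = 1.00 | 20.0 | 80% |

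**Unequal SDs.** A high rho alone does not remove the gain. If loss is proportional to the starting value, the follow-up SD shrinks. For illustration, take k = 0.8 and rho = 0.9:
- change: 1 + 0.64 − 1.44 = 0.20
- adjusted: 0.64 × 0.19 = 0.1216
- ratio: 0.608 × 37/36 = 0.62, against 0.98 at the same rho with equal SDs.

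Simulations of visceral fat used an assumed mean of 180 cm², coefficient of variation 0.35 to 0.45, proportional losses of 25 to 35% against 15 to 20%, and 20 per arm. The SD of the estimated arm difference fell by roughly 4 to 30%, depending mainly on how much percentage loss varies between patients. Both methods estimated the same difference. Under purely additive loss the two SDs were about equal (5.7 and 5.8 cm²), so there was no gain.

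**Chance imbalance.** The standard error of the baseline difference is sqrt(2/20) = 0.316 SD. The probability of a difference above 0.5 SD in either direction is that of |Z| > 0.5/0.316 = 1.58, which is 11% per outcome. It would be 17% if 15 per arm remained (assumed).

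With equal SDs and no true effect, a 0.5 SD imbalance shifts the change-score difference by 0.5 × (1 − rho): 0.30 SD at rho 0.4, 0.20 at 0.6, 0.10 at 0.8 and 0.025 at 0.95. In simulation the adjusted estimate shifted by about 0. Given an imbalance of about that size, the change-score test rejected a true null in 8.4%, 7.3%, 6.1% and 5.5% of trials respectively. Over all randomisations it rejected in about 5%.

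**The case against.** **The planned test is not clearly stated.** This stands. Section 10.2 literally assigns quantitative variables to a paired t test and then falls back on an unpaired rank test. A reader might infer that it prescribes a two-sample t test on changes. That has to be deduced from its reference to differences between groups. The wording is a separate defect, but on either reading no baseline covariate enters.

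**The issue is efficiency, not validity.** This stands. A reader might infer that the planned comparison is biased or inflates false positives. It does not: randomisation makes it unbiased, with about 5% type I error on average. The shift described above is conditional on the imbalance that happens to occur.

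**The gain may be nil.** This stands in part. A reader might infer that every listed outcome loses precision, or that a definite number of power points is at stake. The documents give no correlation or SD for any outcome, and only visceral fat was simulated. Weight or waist could have a slope near 1, leaving nothing to gain. The objection does not show that adjustment does harm: its worst cost is about 37/36 in variance.

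**Robust errors give some of the gain back.** This stands. In the simulations HC3 standard errors cost 1 to 4 power points and rejected a true null about 4 to 5% of the time. That favours ordinary standard errors for the main analysis.

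**This is an exploratory pilot with no power target.** True, and no stated figure is overturned. But 10.2 still applies a significance level to all tests, and a sharper interval is useful in a pilot.

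**Conclusion.** The point holds as a missed and nearly free improvement to the between-arm analysis of every continuous outcome, including liver fat, the first-listed primary variable. The unadjusted change comparison is valid but never materially more precise than the adjusted one, and it passes on (1 − rho) of any baseline imbalance when SDs are equal.

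The size is not fixed by the documents. With equal SDs, the variance saving runs from about 23% at rho 0.5 to none at 0.95. For visceral fat, the reduction in the SD of the estimate is roughly 4 to 30% under proportional loss and zero under additive loss. The documents do not say which applies. They therefore support neither a claim that all outcomes lose precision nor any single figure for power gained.

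**What to change.** In 10.2, for each continuous outcome (liver fat, visceral fat, stiffness, weight, BMI, waist, salivary cortisol), and separately at month 2 and month 6:

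- Make the between-arm analysis a linear model of the follow-up value on arm and that outcome's own baseline value. Report the adjusted difference with its 95% CI.
- Use ordinary standard errors for the main result and HC3 robust errors as a sensitivity analysis.
- Where model conditions fail, use ANCOVA on the log scale or a rank-based ANCOVA in place of the Mann-Whitney fallback.
- Keep paired tests only to describe change within each arm. This also removes the doubt about which t test compares the arms.

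The cost is one paragraph and one degree of freedom. No new data or visits are needed, and no extra patients are excluded, since a change score already requires both values. Writing it in now also prevents a choice to adjust after an imbalance has been seen.

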1.12 Outcome Measures

- Body weight loss
- Visceral fat (measured by the area in squared centimeters at the level of the 3rd vertebrae, using MRI technique)
- Porcentaje de contenido graso del hígado
- Liver stiffness using MR Elastography
- Linear measurements of the adrenal glands
- Salivary cortisol levels

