One of the leading extra-hepatic causes of liver steatosis is metabolic syndrome (MS). Although, multiple definitions of MS exists; the essential components of MS include insulin resistance, increased levels of stress hormones, such as cortisol, and visceral obesity. In the obese population, the hallmarks of a metabolic syndrome are highly prevalent, being peripheral insulin resistance and increase levels of stress hormones the leading causes of organ injury. In such individuals higher levels of cortisol are expected, secondary to an over activated hypothalamic-pituitary-adrenal (HPA) (13, 14). A linear correlation between adrenal gland volume and metabolic syndrome has been demonstrated, with increased adrenal volume in patients under a metabolic syndrome status. However, once these patients are engaged on a treatment regime, leading to weight loss and diminished insulin resistance, the increase in adrenal volume tends to be reversible. Adrenal volume measurements can be achieved using cross-sectional imaging and semi-automated softwares. In clinical practice, adrenal gland dimensions are generally assessed using limb linear measurements on multidetector row computed tomography or magnetic resonance imaging (15,16).

We conducted a prospective longitudinal clinical study to correlate the effects of a very low-calorie-ketogenic diet (PRONOKAL method*), body weight loss and visceral fat reduction, with liver fat fraction, using a new MRI model of fat liver quantification (Ideal IQ**). Additionally, the degree of liver fat and its evolution, during the diet program, will be correlated with liver stiffness using MR Elastography. Adrenal gland measurements will also be made using the linear technique described by Carsin-Vu A. (16) to address its correlation with weight loss, visceral fat and liver steatosis.

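### Section 10.2 names only a paired t test, which does not fit the comparison of two randomised diets, and calls the liver outcome a ratio defined nowhere; most likely a drafting slip, to be corrected before analysis

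*Combined protocol and SAP*

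**What the plan says.** Section 10.2 opens by stating that, for the primary and secondary objectives, "the differences between visits and between groups will be studied". The tests follow in three steps:

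- For continuous outcomes, "the quantitative variables will be compared by means of the Student's t test for paired data".
- If its conditions fail, "we will use the non-parametric Mann-Whitney U test".
- Then: "In the case of comparing paired data, we will use the tests described above, in their version for comparing this type of data".

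The liver outcome appears in 10.2 as "changes in the ratio between liver fat and the degree of steatosis (measured by MRI"). Elsewhere it has other names. Section 9.1.1 gives the primary variable as "Liver fatty infiltration, measured by a MRI technique of fat liver quantification" (Ideal IQ), section 4 speaks of correlating the diet's effects "with liver fat fraction, using a new MRI model of fat liver quantification", and section 1.12 lists, in untranslated Spanish, "Porcentaje de contenido graso" of the liver, that is, a percentage fat content.

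Section 6.2 describes 1:1 randomisation of individual patients from a generated list, with no matching. Section 7.4 plans 20 patients per arm. Section 7.7 foresees dropouts.

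**The concern.** The randomised part of the primary aim (section 5.1) is the contrast between the two diets in liver fat and visceral fat. The one t test named for continuous outcomes is designed for two measurements on the same patient. It suits change between visits but not the contrast between two independent arms.

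Taken literally, the plan leads to one of two poor results. Either patients from different arms are paired arbitrarily, or each arm is tested against its own baseline and the t test never compares the diets. The second is the greater risk, because significance in one arm and not in the other is easily mistaken for a diet effect.

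The liver outcome adds a smaller problem. A primary variable should carry its defined name in the analysis section, and no scale for degree of steatosis is given that could serve as a denominator.

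**Working it through.** **Inputs.** From the documents: 20 per arm (7.4; 20 + 20 = 40, which agrees with the stated total) and significance at 0.05 (10.2; two-sided assumed). Section 7.5 gives no effect size, SD, power or dropout rate, so no power figure of the plan can be reproduced. All effect sizes, missing-scan rates, correlations and SD ratios below are assumptions.

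**Reading A: unpaired between arms, paired between visits.** This is the natural sense of the paragraph. Mann-Whitney is an independent-samples test, and a separate rule for paired data is redundant if the first t test is already paired. Power of the unpaired t test on change uses the noncentral t with 38 df and noncentrality d × √(20/2). For d = 0.5, 0.8 and 1.0 SD of change, power is 34%, 69% and 87%. Nothing is lost on this reading.

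**Reading B: paired across arms.**
- With 20 complete patients per arm and arbitrary pairing (19 df, correlation 0), power is 32%, 67% and 85% at the same effects, and type I error stays at 0.050.
- The p-value depends on the pairing. In one simulated dataset the unpaired p was 0.022, while 10,000 random pairings gave paired p from 0.002 to 0.073.
- The test cannot be run on unequal arms without discarding patients. If each patient lacks a follow-up MRI with probability q, P(unequal) = 1 − Σ P(X = x)², where X is Binomial(20, 1 − q). For q = 5%, 10% and 20% this gives 69%, 79% and 84%.

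**Reading C: paired within each arm only.** Suppose both arms truly change by the same 0.5 SD. Noncentrality is 0.5 × √20 = 2.236 with 19 df, so each arm is significant with probability 0.565. Exactly one arm is significant with probability 2 × 0.565 × 0.435 = 0.49, although the diets do not differ. At a common change of 0.3 or 0.65 SD the figure is 37% or 33%.

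**Liver outcome.** Sections 1.12, 4 and 9.1.1 agree on MRI liver fat, as a fraction or percentage. None defines a ratio of liver fat to degree of steatosis.

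**What baseline adjustment would add.** Let k be the follow-up SD over the baseline SD and ρ the baseline to follow-up correlation. The variance of ANCOVA relative to the change score is

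V = k²(1 − ρ²) / (1 + k² − 2ρk), times (1 + 1/36) for estimating the slope, with 37 df.

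At 0.8 SD of change and 20 complete patients per arm, noncentrality is 2.530 / √(V × 37/36). Example, k = 1 and ρ = 0.5: V = 0.75, noncentrality 2.881, power 80%. Worst cell, k = 1.25 and ρ = 0.8: V = 0.5625/0.5625 = 1, noncentrality 2.495, power 68.1% against 69.3%.

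| k | Power, ρ from 0.3 to 0.9 | 95% CI width relative to change score |
|---|---|---|
| 0.75 | 90-95% | 0.69-0.76 |
| 1.00 | 70-85% | 0.82-0.99 |
| 1.25 | 68-78% | 0.90-1.015 |

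The gain is large if the SD shrinks on treatment and vanishes when ρk is near 1.

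**The case against.** The strongest reply is that the paragraph nearly corrects itself. Its fallback test and its separate rule for paired data make sense only if the first t test was meant as unpaired, and leftover Spanish in sections 1.12 and 8.1 makes a translation error plausible. That stands, and it is why the point is a wording correction. It does not remove the need, because the test for the primary contrast should be stated and not inferred.

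It can also be said that a fat fraction is itself a ratio of signals (section 4 describes its calculation) and that no rival liver variable exists. That stands too: a reader might infer that the primary endpoint is undefined, but the other sections settle what is meant.

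Three further inferences are not supported:

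- **That the plan would inflate false positives.** Even under reading B, type I error stays at 0.050. The harm lies in arbitrariness and in not being able to run the test.
- **That 69-84% of such trials would fail.** Those figures belong only to the unlikely reading B, with invented missing-scan rates taken as equal in both arms. Section 7.7 makes unequal arms possible. Its and/or wording does not settle whether a patient who misses a control visit is a dropout, nor how patients with one follow-up MRI are analysed.
- **That change scores are biased.** Under randomisation they are not. ANCOVA is a gain in efficiency, and preferring it is a separate matter from correcting the error.

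**Conclusion.** Section 10.2 is wrong as written: the only t test it names does not fit the between-diet comparison, and its name for the liver outcome matches no defined variable. Most likely both are drafting or translation slips. On the probable reading the statistical cost is nil. The material risk is reading C, where separate within-arm tests could suggest a diet difference that does not exist, in 49% of trials under the assumed common change of 0.5 SD with 20 complete patients per arm.

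The protocol calls itself an exploratory pilot (7.5) and the intent can be recovered, so this is not a fatal flaw. It should be corrected before analysis, because the trial is open-label and 10.2 applies a 0.05 threshold to every test. Confidence in the textual point is high; the numerical sizes rest on the stated assumptions.

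**What to change.** Reword section 10.2 as follows.

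1. Replace the ratio with MRI liver fat fraction (%), consistent with sections 1.12, 4 and 9.1.1.
2. For liver fat and visceral fat area, state one governing between-arm analysis: ANCOVA of the follow-up value on arm and baseline value, at month 2 and at month 6, reporting the between-arm difference with its 95% CI. Mann-Whitney on change is a sensitivity analysis. The minimum acceptable correction is to specify the t test for independent samples, in place of paired data, for between-arm comparisons of change.
3. For the other quantitative variables, compare arms by the independent-samples t test on change, or Mann-Whitney if its conditions fail.
4. Use the paired t test, or Wilcoxon signed-rank, for changes between visits within an arm, and state that these within-arm results are not evidence of a difference between diets.

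The cost is rewording only. The flow chart in 9.2.2 already schedules MRI at baseline, month 2 and month 6, so no new data, visits or patients are needed. ANCOVA uses one degree of freedom and, in the worst case computed, costs about 1 point of power.

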1.15 Funding

We were awarded a grant from PronoKal Group® to partially fund this study, where MR image acquisition and post-processing costs will be covered. The leading investigators, free of charge, will do all data analysis and manuscript writing.

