7.7 Criteria for withdrawal or dropouts

Patients who do not attend the control visits and/or have not undergone at least two MRIs (baseline and control after the end of ketosis or at month 6) will be considered as dropouts.

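### Section 10.2 sends any failure of the t-test conditions to Mann-Whitney U, with no unequal-variance method, no defined trigger and no between-arm estimate

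*Combined protocol and SAP*

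**What the plan says.** Section 10.2 (Analysis of objectives) covers changes between visits and between groups in liver fat, stiffness, salivary cortisol, weight, BMI, waist and visceral fat. For quantitative variables it names Student's t test, worded as the paired form. If the conditions for that test are not met, "we will use the non-parametric Mann-Whitney U test". A closing sentence says that paired comparisons will use the paired versions of these tests. This suggests that the first sentence was meant to name the independent-samples test. The conditions are not listed, no check of them is named, and unequal variance is not separated from non-normality. The level is 0.05 for every test, with sidedness not stated.

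The first end point in section 9.1.3 is "Reduction of fat infiltration into the liver between the baseline visit and 2 months (or end of the ketosis stage"), and again from baseline to month 6. Visceral fat and weight are treated in the same way. Neither section says whether a reduction is summarised by a mean, a median or something else. Section 10.1 promises 95% confidence intervals for the description of continuous variables. Section 10.2 promises none for the difference between arms.

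Sections 6.2 and 7.4 give 1:1 allocation with 20 patients per arm. Section 6.4 states that there is no masking. Section 1.15 adds: "The leading investigators, free of charge, will do all data analysis and manuscript writing".

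**The concern.** The two-sample Student test assumes normality and equal variances. A rank test is a reasonable response to failure of the first. It does not repair failure of the second when the question is how much more one arm lost than the other. Mann-Whitney tests whether a patient from one arm tends to exceed a patient from the other, that is, whether P(X > Y) = 0.5. With unequal spread and skewness, that probability can differ from 0.5 while the mean reductions are equal.

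Both features are plausible here, although this is inference, because the documents report no SDs:

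- **Spread.** VLCK patients move through phases according to individual weight loss (8.1). Their first control may come before month 2, while controls are seen at month 2 (9.2.1).
- **Skewness.** Eligibility (7.2) sets a minimum BMI but no minimum liver fat, so some patients have little liver fat to lose.

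At stake is what a significant result means. Under the written rule, one outcome may be tested for a difference in means and another for a shift in ranks, and the rank result comes with no estimate on the scale of the end point.

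**Working it through.** **Inputs from the documents.** 20 per arm (7.4), 1:1 (6.2), level 0.05 (10.2; two-sided assumed). The sample-size rationale is only that "it has been estimated that 20 patients per group will be sufficient to analyze results", with no SD, effect size or power, so there is no planned figure to reproduce.

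**Assumptions.** The target is the difference in mean change. The SD ratio between arms is 1 to 4, and skewness of the changes is 0 to 2. Section 7.7 defines dropouts but gives no rate, so unequal completer numbers are also assumed.

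**Method.** Simulation with a true mean difference of 0 and 40,000 trials per cell.

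- Mann-Whitney: z = (|U − n₁n₂/2| − 0.5) / √(n₁n₂(n₁+n₂+1)/12). At 20 v 20 the centre is 200 and the denominator is √(400 × 41/12) = 37.0.
- Welch: t = (x̄₁ − x̄₂) / √(s₁²/n₁ + s₂²/n₂). With equal arms this equals the pooled t statistic; only the degrees of freedom differ. At SD ratio 2 they are 19 × (4+1)²/(4²+1²) = 27.9, against 38 for the pooled test.

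**Step 1, calibration.** With identical distributions at 20 v 20, Mann-Whitney rejects in 4.9 to 5.0% of trials, as it should.

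**Step 2, planned size, SD ratio 2.** The last column applies an assumed version of the rule (Levene or Shapiro p < 0.05 leads to Mann-Whitney, otherwise pooled t; 4,000 trials).

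| Changes | Mann-Whitney | Welch | Full rule |
|---|---|---|---|
| Normal | 5.9% | 5.1% | 5.1% |
| Gamma, skewness 1 | 8.4% | 5.2% | 8.2% |
| Gamma, skewness 1.41 | 11.2% | 5.4% | 11.4% |
| Exponential, skewness 2 | 19.1% | 6.1% | 19.1% |

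The pooled t test stays at 5.3 to 6.2% in these cells. The assumed checks trigger the switch in 75%, 85%, 94% and 99% of trials respectively. The Monte Carlo standard error at 11.2% is √(0.112 × 0.888/40,000) = 0.16 points; for the full rule at 11.4% it is √(0.114 × 0.886/4,000) = 0.5 points.

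**Step 3, other spreads, Mann-Whitney, 20 v 20.**

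| Changes | SD ratio 1.5 | 2 | 3 |
|---|---|---|---|
| Normal | 5.3% | 5.9% | 6.8% |
| Skewness 1 | 6.3% | 8.4% | 11.3% |
| Skewness 1.41 | 8.1% | 11.2% | 15.9% |
| Skewness 2 | 12.3% | 19.1% | 25.7% |

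With normal data the rate is still 7.5% at SD ratio 4, and reaches 11.7% only as the ratio goes to infinity. Skewness alone does not fix the rate: a lognormal with nominal skewness 1.75 gives 11.7% at ratio 2.

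**Step 4, unequal completers, normal data.** With 14 v 20 and the smaller arm more variable, Mann-Whitney gives 6.7%, 8.5% and 9.5% at SD ratios 2, 3 and 4, and Welch 5.0%. With the larger arm more variable, Mann-Whitney gives 4.1 to 4.8%, so there is no inflation.

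**Step 5, direction.** At skewness 1.41, SD ratio 2 and 20 v 20, with right-skewed reductions, P(X > Y) is 0.44 for the more variable arm. Rejections favour the less variable arm in 11.1% of trials and the more variable arm in 0.5%.

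**The case against.** A t test with a rank fallback is conventional, and this is an exploratory pilot. Several objections have force.

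- **Unequal spread alone does not double the error rate.** A reader might infer that it does. At 20 v 20 with symmetric changes the rate is 5.9% at SD ratio 2. This objection stands in full.
- **Mann-Whitney is not always the worse test.** With normal changes and unequal arms it can be nearer 5% than Student: 7.1% v 8.2% with 14 (wider arm) v 20, and 4.2% v 3.0% with 20 (wider arm) v 14, both at SD ratio 2. The case against it rests on the skewed cells.
- **The target is not stated.** If the diets had identical effects, Mann-Whitney would hold its level. In the skewed cells the distributions really do differ, so a rejection is false only as a statement about means. This stands, and it is also a reason to state the target, because under the present rule the target changes with the data.
- **Mann-Whitney can be more powerful.** With gamma changes (skewness 1.41), equal spread, 20 v 20 and an assumed 0.8 SD shift, power is about 80%, against about 70% for Welch. This is a real cost of the change.

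A reader might also infer that the fallback favours the sponsor's diet, or that the investigators would pick the test to suit the result. The documents support neither. If the VLCK arm is the more variable one and its reductions are right-skewed, the excess favours control. Section 10.2 states a conditional rule, not a free choice. What can fairly be said is that the trigger is undefined in an unmasked study analysed by its own investigators.

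**Conclusion.** The point holds in a limited form. What the text itself shows is that section 10.2 offers no unequal-variance method, does not define when the switch occurs, lets the tested hypothesis depend on the data, and promises no between-arm estimate of the reduction.

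The size depends on assumptions that the documents neither state nor exclude: a difference in means as the target, an SD ratio of about 2, and skewness. On those terms Mann-Whitney's false-positive rate runs from about 6% (symmetric) to 19% (skewness 2) at 20 v 20, against 5 to 6% for Welch. Doubling needs skewness of about 1.4 at SD ratio 2, or about 1 at SD ratio 3. For symmetric data with unequal completers, it would need an SD ratio of 4 or more in the smaller arm.

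Because the excess points towards the less variable arm when reductions are right-skewed, the rank test could also obscure a modest mean benefit in the more variable arm. This should be changed before analysis, but it does not threaten the trial.

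**What to change.** In section 10.2:

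1. State the target as the between-arm difference in mean change from baseline, at month 2 (or end of ketosis) and at month 6.
2. Remove the data-dependent switch and name one between-arm analysis: a linear model of change on arm and the baseline value, with HC3 standard errors. If no adjustment is wanted, name Welch's t test instead. Without the covariate, HC3 gives Welch's standard error with nᵢ − 1 in place of nᵢ, which is √(20/19) = 1.026 times as large at 20 per arm. The adjusted model itself was not simulated here.
3. Report the difference with a 95% CI, and a bootstrap CI as the check for skewness.
4. Keep Mann-Whitney as a labelled sensitivity analysis.
5. Correct the default so that the paired t test applies to within-arm changes only.

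The cost is a few sentences and no new data, since the baseline values are already collected (9.2.1). If changes are skewed with equal spread there is some loss of power (about 70% v 80% in the assumed case above), which the sensitivity analysis partly offsets. Welch's test is not exact either: with 14 (wider arm) v 20, exponential changes and SD ratio 2 it gives 7.5%, against 18.1% for Mann-Whitney. That is why the bootstrap check is worth including.
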